#### MDRD Equation:

$$\text{eGFR (mL/min/1.73 m}^2\text{)} = 175 \times (\text{serum creat})^{-1.154} \times (\text{age})^{-0.203} \times (0.742 \text{ [if female]}) \times (1.212 \text{ [if African American]})$$

At the discretion of the investigator a measured creatinine clearance, as determined by a 24-hour urine collection, may be used in place of, or in conjunction with, the estimate of the eGFR.

15. Has a history of significant multiple and/or severe allergies (eg, food, drug, latex allergy), or has had an anaphylactic reaction or significant intolerance (ie, systemic allergic reaction) to prescription or non-prescription drugs or food.

16. Is positive for hepatitis B surface antigen, hepatitis C antibodies or HIV.
17. Had major surgery, donated or lost 1 unit of blood (approximately 500 mL) within 4 weeks prior to the prestudy (screening) visit.
18. Has evidence or history of a primary DSM-5 axis I psychiatric diagnosis other than schizophrenia or schizoaffective disorder per the allowed DSM-5 criteria within 1 month of screening (applies to participants with schizophrenia only).
19. Is mentally or legally incapacitated, has significant emotional problems at the time of prestudy (screening) visit or expected during the conduct of the study or has a history of clinically significant psychiatric disorder of the last 5 years. Participants who have had situational depression may be enrolled in the study at the discretion of the investigator (applies to healthy participants only).
20. Is at imminent risk of self-harm, based on clinical interview and responses on the C-SSRS, or of harm to others in the opinion of the investigator. Participants must be excluded if they report suicidal ideation with intent, with or without a plan or method (eg, positive response to item 4 or 5 in assessment of suicidal ideation on the C-SSRS) in the past 2 months or suicidal behavior in the past 6 months (applies to participants with schizophrenia only).
21. Is at imminent risk of self-harm, based on clinical interview and responses on the C SSRS, or of harm to others in the opinion of the investigator. Participants must be excluded if they report suicidal ideation with intent, with or without a plan or method (eg, positive response to item 4 or 5 in assessment of suicidal ideation on the CSSRS) in the past 5 years or suicidal behavior in their lifetime (applies to healthy participants only).

#### **Prior/Concomitant Therapy**

22. Has received treatment with clozapine for schizophrenia or treatment with monoamine oxidase inhibitors within 3 months of screening or cariprazine within 2 months of screening.
23. Has received a parenteral depot antipsychotic medication within 3 months of screening.
24. Is unable to refrain from the use of co-medication with a moderate or strong inhibiting or inducing effect on CYP3A and/or CYP2C9 beginning approximately 2 weeks or 5 half-lives, whichever is longer, prior to administration of the initial dose of trial drug and throughout the trial or is unable to refrain from the use of sensitive substrates of CYP2B6. (see Section 6.5).

#### **Prior/Concurrent Clinical Study Experience**

25. Has participated in another investigational study within 4 weeks (or 5 half-lives, whichever is greater) prior to the prestudy (screening) visit. The window will be derived from the date of the last visit in the previous study.

## Diagnostic Assessments

Not Applicable.

## Other Exclusions

26. Is under the age of legal consent.
27. Has been in incarceration or imprisonment within three months prior to screening.
28. Is a current smoker (applies to healthy participants only) or is a smoker (applies to participants with schizophrenia only) that does not agree to follow the smoking restrictions as defined by the CRU.
29. Consumes greater than 3 glasses of alcoholic beverages (1 glass is approximately equivalent to: beer [354 mL/12 ounces], wine [118 mL/4 ounces], or distilled spirits [29.5 mL/1 ounce]) per day. Participants who consume 4 glasses of alcoholic beverages per day may be enrolled at the discretion of the investigator.
30. Consumes excessive amounts, defined as greater than 6 servings (1 serving is approximately equivalent to 120 mg of caffeine) of coffee, tea, cola, energy drinks, or other caffeinated beverages per day.
31. Is a regular user of cannabis, any illicit drugs or has a history of drug (including alcohol) abuse within approximately 3 years. Participants must have a negative UDS (with the exception of cannabis and/or prescribed concomitant medications permitted at the discretion of the PI and Sponsor) prior to randomization.
32. Presents any concern by the investigator regarding safe participation in the study or for any other reason the investigator considers the participant inappropriate for participation in the study.
33. Is or has an immediate family member (eg, spouse, parent/legal guardian, sibling, or child) who is investigational site or Sponsor staff directly involved with this study.

## 5.3 Lifestyle Considerations

### 5.3.1 Meals and Dietary Restrictions

#### 5.3.1.1 Diet Restrictions

Fasting requirements for study procedures, such as but not limited to laboratory safety evaluations are specified in Appendix 2.

On full **PK sampling days**, participants will fast from all food and drinks, except water, for at least 8 hours prior to study drug administration until 1-hour postdose. Participants will fast from all food and drinks except water between study drug administration and the first scheduled meal. Meals and snack(s) will be provided by the investigator at time points

indicated in the Schedule of Activities. Participants will fast from all food and drinks except water between meals and snacks. The caloric content and composition of meals will be the same on each full PK sampling day in each panel (for this study the meal content should be consistent within a given clinical site). After the 24-hour postdose procedures have been completed, subsequent meals and snacks will be unrestricted in caloric content, composition and timing.

Water will be provided during study drug administration. Water will be restricted 1 hour prior to and 1 hour after study drug administration.

On **all other days**, participants will fast from all food and drinks, except water, for at least 8 hours prior to study drug administration. Participants will remain fasted until 1-hour postdose. Meals and snacks will be unrestricted in caloric content, composition and timing.

Standard meals on Day -1 will be time-matched to Day 1.

Each study drug administration will need to be taken with water. Water will be restricted 1 hour prior to and 1 hour after study drug administration.

### **5.3.1.2 Fruit Juice Restrictions**

Participants will refrain from the consumption of grapefruit juice, grapefruits, and grapefruit products beginning approximately 2 weeks prior to administration of the initial dose of study drug, throughout the study and until the poststudy visit.

On full **PK sampling days**, participants will refrain from the consumption of all fruit juices 24 hours prior to study drug administration.

On **all other days** during the study, the consumption of all fruits and fruit juices (except for grapefruit, grapefruit juices, and grapefruit products) is allowed.

### **5.3.2 Caffeine, Alcohol, and Tobacco Restrictions**

#### **5.3.2.1 Caffeine Restrictions**

Participants will refrain from consumption of caffeinated beverages or xanthine-containing products from 12 hours prior to the prestudy and poststudy visits.

On full **PK sampling days**, participants will be permitted to consume approximately 2 units of caffeinated beverages or xanthine-containing products only between 1 hour and 2 hours postdose. Otherwise, participants will refrain from consumption of such products 8 hours prior to study drug administration until the last PK assessment is complete.

On **all other days**, caffeinated beverages or xanthine-containing products will be limited to no more than 6 units per day (1 unit = 120 mg of caffeine).

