- Day -1 (triplicate measurements): Time-matched to 8, 16 and 24 hours postdose vital signs.
- Day 1, Day 4 and Day 7: 8, 16 and 24 hours postdose
- Day 9: Time-matched to 24-hour postdose vital signs

d. Orthostatic assessments in HR and BP will follow semi-recumbent vital sign assessments. Participants should be standing for approximately 2 minutes prior to the orthostatic assessments. Orthostatic HR and BP measurements will be obtained on:

- Day -1: Time-matched to 8, 16 and 24 hours postdose orthostatic vital signs.
- Day 1, Day 4 and Day 7: 8, 16 and 24 hours postdose
- Day 9: Time-matched to 24-hour postdose orthostatic vital signs

e. Scheduled assessments are completed predose on dosing days and at any time on non-dosing days.

f. Single 12-lead safety ECG measurements will be taken at all postdose timepoints. On the following days, specific timepoints are noted:

- Day 1: Triplicate measurements within 2 hours prior to dosing
- Day 1 and Day 4: 8, 16 and 24 hours post-dose

Part 2 Panel E/G Titration Regimen 2 MK-8189/matching placebo 24 mg x 7 days														
Scheduled Day	Screening	Washout	Intervention										Poststudy	Notes
	-6	-2	-1	1	2	3	4	5	6	7	8	9	~14	
g.	Screening UDS is mandatory; any additional UDS are conducted per site SOP. UDS prior to randomization will be done on the day of admission.													
h.	Additional BARS, AIMS and SAS assessments will be conducted as soon as possible when there are observed or reported complaints of dystonia and/or akathisia (See Section 8.3.6).													
i.	MK-8189 plasma PK sample collection:													
	
 
Day 1: predose, 2, 6, 8, 10, 12 and 16 hours postdose
 
Day 2 and Day 3: predose, 2, 6 and 8 hours postdose
 
Day 7: predose, 2, 6, 8, 10, 12, 16, 24, 36 and 48 hours postdose
 
Optional sample when signs of dystonia and/or akathisia occur.
 
Leftover main study plasma will be stored for future biomedical research if the participant consents to future biomedical research.
 
													
j.	This sample will be drawn for CYP2C9 and for planned analysis of the association between genetic variants in DNA and drug response. If the IRB/IEC does not approve of the planned analysis of the association between DNA variation and drug response, or if there is a local law or regulation prohibiting the same, data analysis will be limited to CYP2C9. Leftover extracted DNA will be stored for future biomedical research.													

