#### **Type of Participant and Disease Characteristics**

1. Is in good health based on laboratory safety tests obtained at the screening visit. Appendix 2 provides a table of laboratory safety tests to be performed. Appendix 10 provides an algorithm for the assessment of out of range laboratory values.

2. Has a BMI  $\leq 40 \text{ kg/m}^2$  (participants with schizophrenia) or  $\leq 32 \text{ kg/m}^2$  (healthy participants), inclusive. See Section 8.3.1 for criteria on rounding to the nearest whole number. BMI = weight (kg)/height (m) $^2$ .
3. Has no clinically significant abnormality on 12-lead safety ECG performed at the prestudy (screening) visit and/or prior to randomization. The Day 1 predose assessment (prior to randomization) is based on the mean of the triplicate measures. Note: The QTcF duration must be  $\leq 450$  msec and the PR interval  $< 230$  msec. Repeat 12-lead safety ECGs may be performed in participants whose parameters are, per investigator discretion, minimally outside the designated range. Appendix 9 provides a table of the 12-Lead Electrocardiogram Abnormality Criteria.
4. Has a normal resting BP (systolic BP is  $\geq 90$  mmHg and  $\leq 140$  mmHg; diastolic BP is  $\geq 60$  mmHg and  $\leq 90$  mmHg) and normal resting heart rate ( $\geq 45$  beats per minute [bpm] and  $\leq 100$  bpm) in the semirecumbent position at the prestudy (screening) visit and/or prior to randomization. Repeat evaluations may be done if the values for a participant are, per investigator discretion, minimally outside the designated range. The assessment prior to randomization is based on the mean of the triplicate measures for the Day -1 8 hour time-matched assessment. Participants may be included if values are outside the normal range but considered not clinically significant per investigator discretion.
5. Participants with hypothyroidism, diabetes, high BP, chronic respiratory conditions or other mild forms of these medical conditions could be considered as candidates for study enrollment if their condition is stable and the prescribed dose and regimen of medication is stable for at least 3 months prior to screening and there are no expected changes in comedication during the study.
6. Has regular bowel movements and, in the opinion of the investigator, no clinically significant diarrhea or constipation.

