#### **8.3.2.1 Resting Vital Signs**

##### **Vital Sign Measurements (Heart Rate and Blood Pressure)**

Participants should be resting in a quiet setting without distractions in a semirecumbent position for at least 10 minutes prior to having VS measurements obtained. Semirecumbent VS will include HR, systolic and diastolic BP, respiratory rate and body temperature at timepoints indicated in the SoA. The correct size of the BP cuff and the correct positioning on the participants' arm is essential to increase the accuracy of BP measurements.

The predose (baseline) HR and BP will be triplicate measurements, obtained at least 1 to 2 minutes apart on Day -1 as indicated in the SoA. The mean of Day -1 time-matched triplicate measurements will be used as the baseline to calculate change from baseline for postdose safety evaluations (and for rechecks, if needed). Screening and postdose VS measurements will be single measurements.

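### Caffeine is almost uncontrolled on Day -1, the heart-rate and blood-pressure baseline day, but restricted on the PK days compared with it

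*Combined protocol and SAP*

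**What the plan says.** Section 5.3.2.1 has two in-study caffeine rules. The first, for full PK sampling days, sets a small allowance: "participants will be permitted to consume approximately 2 units of caffeinated beverages or xanthine-containing products only between 1 hour and 2 hours postdose". Outside that hour it asks for abstinence over a wide window, in these words: "participants will refrain from consumption of such products 8 hours prior to study drug administration until the last PK assessment is complete". The second rule covers every remaining day and has no times attached: "caffeinated beverages or xanthine-containing products will be limited to no more than 6 units per day (1 unit = 120 mg of caffeine"). A further abstinence rule runs only "from 12 hours prior to the prestudy and poststudy visits", so it does not reach Day -1.

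Section 8.3.2.1 makes Day -1 the heart-rate and blood-pressure baseline: "The mean of Day -1 time-matched triplicate measurements will be used as the baseline to calculate change from baseline for postdose safety evaluations". Sections 9.1, 9.4 and 9.6 say the same. Footnote c of each schedule in Section 1.3 puts the Day -1 readings at the clock times of the 8-, 16- and 24-hour postdose readings. Inclusion criterion 4 uses one of them again: "The assessment prior to randomization is based on the mean of the triplicate measures for the Day -1 8 hour time-matched assessment".

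Food is aligned across the two days: "Standard meals on Day -1 will be time-matched to Day 1". There is no matching sentence for caffeine.

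**The concern.** Vital signs are part of the primary endpoint (Section 3). A time-matched baseline is meant to remove everything that varies with clock time, so that what remains is drug effect and noise. The plan matches reading times and meals but leaves caffeine out. The day that provides the baseline then follows a looser rule than the days compared with it, and the mismatch goes straight into change from baseline.

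The Day -1 cap also restrains hardly anyone. Exclusion 30 already removes people who take more than 6 servings of about 120 mg a day, so Day -1 permits habitual intake while PK days cut it to about 2 units. Unadjusted individual values matter here because Section 6.6 lists vital signs among the data behind each participant's titration decision.

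**Working it through.** The plan has no figure of its own to reproduce on this point. The check is a comparison of schedules plus simple arithmetic.

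**1. Which days fall under which rule** (Sections 1.3.1 to 1.3.5, footnotes on vital signs and PK samples)

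| Schedule | Timed on-treatment HR/BP days | PK days | HR/BP days outside the PK-day rule |
|---|---|---|---|
| Panel A | 1, 4, 7 | 1, 4, 7 | -1 |
| Panel B | 1, 4, 7 | 1, 2, 3, 7 | -1 and 4 |
| Panel C | 1, 2, 3, 7 | 1, 2, 3, 7 | -1 |
| Panel D/F | 1, 4, 7, 13 | 1, 4, 7, 13 | -1 |
| Panel E/G Regimen 1 | 1, 4, 10 | 1, 4, 10 | -1 |
| Panel E/G Regimen 2 | 1, 4, 7 | 1, 2, 3, 7 | -1 and 4 |
| Panel E/G Regimen 3 | 1, 2, 3, 9 | 1, 2, 3, 9 | -1 |

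The plan does not define a full PK day. Every PK day with timed HR/BP readings is sampled to at least 16 hours, so I count those as full. Regimen 2 takes timed readings on "Day 1, Day 4 and Day 7: 8, 16 and 24 hours postdose" but has no PK samples on Day 4.

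**2. Amount allowed.** Day -1: 6 × 120 = 720 mg. PK day: 2 × 120 = 240 mg. The difference is 480 mg, and the ratio is 720/240 = 3.

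**3. Timing**, in hours from the (matched) dose. The abstinence before the Day 1 dose starts at hour 24 − 8 = 16 of Day -1. The last caffeine on a PK day is at hour 2. The shortest permitted gaps from caffeine to reading are:

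| Reading | Day -1 | PK day |
|---|---|---|
| 8 h | no minimum | 8 − 2 = 6 h |
| 16 h | no minimum (restriction starts then) | 16 − 2 = 14 h |
| 24 h | 24 − 16 = 8 h | 24 − 2 = 22 h |

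If Day -1 caffeine were taken only with scheduled meals (about 1, 4, 8 and 12 hours, each after that timepoint's procedures), the gaps would be 8 − 4 = 4 h and 16 − 12 = 4 h. These are still shorter than 6 h and 14 h.

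**4. Illustration of direction.** This assumes first-order elimination with a caffeine half-life h of 3 to 7 hours, which is not in the documents. Caffeine remaining at time T is the sum of dose × 2^(−(T − t)/h). For a PK day at 8 h with h = 3, this gives 240 × 2^(−6.5/3) = 53 mg. Ranges run over h = 3 to 7.

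| Pattern | 8 h (mg) | 16 h (mg) | 24 h (mg) |
|---|---|---|---|
| PK day: 240 mg at 1.5 h | 53–126 | 8–57 | 1–26 |
| Day -1: 240 mg at each of 1.5, 4.5 and 7.5 h | 374–524 | 59–237 | 9–108 |
| Day -1: 240 mg at each of 1.5, 12.5 and 15.5 h | 53–126 | 329–455 | 52–206 |
| Day -1: none | 0 | 0 | 0 |

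Heavy use on Day -1 leaves more caffeine at baseline than on treatment. No use on Day -1 leaves less. The third pattern is an extreme: dosing is in the morning, so those intakes fall late in the evening.

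**The case against.** The strongest reply is that the study is randomised, double-blind and placebo-controlled, and both arms follow the same caffeine rule. Any distortion of the Day -1 baseline is expected equally in placebo, and raw values are summarised as well. This stands: a difference between active and placebo in change from baseline is not biased on average. It does not fully answer the point, because Section 9.6 specifies summary statistics and plots of change from baseline and no placebo contrast. Table 2 gives only 4 placebo participants per schizophrenia panel and 2 per healthy panel. Titration decisions use individual values.

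Second, six units is a ceiling, not an expected intake. This also stands, and it is why the direction is open.

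Third, the eligibility use of the 8-hour reading is of little consequence. Criterion 4 allows repeats and investigator discretion. I agree and give it no weight.

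A reader might also infer several stronger things that the documents do not support:

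- That drug-related rises will be hidden. This needs high Day -1 intake and a pressor or heart-rate effect of caffeine, and the documents establish neither.
- That the bias can be stated in mmHg. No effect size or intake data are given.
- That the monkey telemetry findings make this urgent. Section 4.3.2 judges those heart-rate and blood-pressure changes not relevant to humans.
- That baseline QTc is affected in the same way. The ECG baseline is Day 1 predose, inside the 8-hour abstinence.
- That meals are uncontrolled on Day 4 of Regimen 2. Section 5.3.1.1 reads that way for non-PK days, but footnote a of Section 1.3.4 fixes meal times from Day -1 through Day 8. The two need reconciling, nothing more.

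**Conclusion.** The mismatch in the rule is certain. Day -1 allows three times the caffeine of a PK day (720 against about 240 mg), untimed for about its first 16 hours. That period contains the 8-hour baseline and runs up to the 16-hour one. The 24-hour baseline is largely protected by the 8 hours of required abstinence, though its minimum gap is 8 hours against 22.

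The effect on heart rate and blood pressure is of unknown size and can go either way. Change from baseline would be understated if Day -1 intake is high and caffeine raises these measures. It would be overstated, on the same assumption, if Day -1 intake is below what PK days allow.

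Day 4 of Regimen 2 has the same cap as Day -1, so for change from baseline its rule is currently like-for-like. It differs from that regimen's own Days 1 and 7 and from Day 4 of Regimen 1, although the plan specifies no formal contrast between them.

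This is an avoidable weakness in a descriptive primary endpoint. It does not threaten the randomised comparison, but it is worth correcting because correction is cheap.

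**What to change.** In Section 5.3.2.1, for the remaining Part 2 panels, apply the PK-day caffeine rule to Day -1, with times taken from the matched Day 1 dose time and starting 8 hours before it. Apply it also to every day with timed 8-, 16- and 24-hour vital signs, which adds Day 4 of Titration Regimen 2. The two changes belong together: if only Day -1 were tightened, Day 4 would become the mismatched day. Reconcile the meal sentence for non-PK days in Section 5.3.1.1 with footnote a of the schedules. Part 1 is clinically complete, so report the limitation there.

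The change takes a sentence or two in an amendment and adds no procedures or participants. Participants have one extra day of limited caffeine, or two in Regimen 2. Those with schizophrenia are already confined from Day -6. Healthy elderly participants need only be domiciled by Day -1, so for them the hours before the matched dose time may rest on instruction. The permitted difference between baseline and on-treatment days falls from 480 mg to 0.

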### **5.3.2.2 Alcohol Restrictions**

Participants will refrain from consumption of alcohol 24 hours prior to the prestudy and poststudy visits. During the in-house period, consumption of alcohol is not allowed. At all other times, alcohol consumption is limited to no more than approximately 3 alcoholic beverages or equivalent (1 glass is approximately equivalent to: beer [354 mL/12 ounces], wine [118 mL/4 ounces], or distilled spirits [29.5 mL/1 ounce]) per day.

### **5.3.2.3 Tobacco Restrictions**

Participants will follow the smoking restrictions (and if applicable, the use of nicotine/nicotine-containing products) defined by the CRU.

### **5.3.3 Activity Restrictions**

Participants will avoid unaccustomed strenuous physical activity (ie, weight lifting, running, bicycling, etc.) from the prestudy (screening) visit until administration of the initial dose of study drug, throughout the study and until the poststudy visit.

## **5.4 Screen Failures**

Screen failures are defined as participants who consent to participate in the clinical study but are not subsequently randomized in the study. A minimal set of screen failure information may be included, as outlined in the eCRF entry guidelines. Minimal information may include demography, screen failure details, eligibility criteria, and any AEs or SAEs meeting reporting requirements.

